A crucial element of PROM development is the involvement of patients. This study will ground its development in existing qualitative research of rUTI patient experiences as well as conducting cognitive interviews with rUTI patients to obtain their perspective on whether the PROM questions are appropriate and valid for the population and their experiences of rUTI. Following this, pilot data collection of the PROMs alongside existing standardised measures of contextually relevant health aspects (e.g. pain) will be conducted to perform further statistical validity checks. The cognitive interviewing and piloting of the PROMs may include a mild risk of anxiety or discomfort due to the sensitive nature of some questions and need to reflect on potentially challenging experiences. Participants will maintain the right to withdraw at any point and will be encouraged to seek support from their GP/healthcare professional if needed.

Research Questions:

Primary aims:

1. To develop a patient-reported outcome measure of rUTI symptoms.
2. To develop a patient-reported outcome measure of rUTI impact.

Secondary aims:

1. To validate the rUTI symptom PROM by conducting statistical tests of its internal consistency, test-retest reliability, construct validity and criterion validity.

2. To validate the rUTI impact PROM by conducting statistical tests of its internal consistency, test-retest reliability, construct validity and criterion validity.

Design and Procedure:

An initial rUTI symptom scale and rUTI impact questionnaire have been developed based on existing qualitative research and literature review. The rUTI Symptom Scale includes a UTI-related symptom intensity subscale, and a UTI-pain intensity sub-scale. This PROM is designed to assess symptom intensity over the past 24 hours. The rUTI Impact Questionnaire includes a personal wellbeing subscale (covering psychological wellbeing and sleep/exercise disruption), a social subscale (covering social impact, isolation and anxiety), a work impact subscale, a sexual subscale (covering sexual impact and pain), and a patient satisfaction subscale. This PROM is designed to assess rUTI impact over the past two weeks.

A three-stage methodology will be employed:

(1) Expert screening for content validity

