The rest of the survey will present a series of questionnaires to the participant. Two will be the new rUTI PROMs which we have developed and refined, and there will also be a number of existing standardised measures which measure similar concepts of symptom intensity and health impact: the symptom severity subscale of the UTI Symptom Assessment (Clayson et al., 2005), Numerical Pain Rating Scale (Jensen & Karoly, 2011), UCLA Loneliness Scale Version 3 (Russell, 1996), Work Productivity and Activity Impairment questionnaire (Reilly et al., 1993), Female Sexual Distress Scale – Revised (Derogatis et al., 2008), Patient Satisfaction Questionnaire Short-Form (Marshall & Hays, 1994), Generalised Anxiety Disorder – 7 (Spitzer et al., 2006), and Patient Health Questionnaire – 9 (Kroenke et al., 2001). It is explained in the Information Sheet that the participant may be asked questions which seem to measure the same thing; this is due to the inherent similarity in some of the measures and the participant should continue to answer all questions in the survey. It is expected that the total survey will take the participants approximately 30 minutes to complete, which is noted in the Information Sheet.

At the end of the survey, the participant will be shown a Debrief Form which provides them with the aforementioned recommended links to access rUTI or mental health support should they need/want it, and reminds them that in 24 hours' time they will receive an email with a link to access and complete the Part 2 survey. The link in this email will be unique for each participant, linking their Part 1 and Part 2 responses in REDCap.

The Part 2 survey, to be completed approximately 24 hours' after Part 1, follows the exact same procedure as in Part 1, with the wording updated in the Participant Information Sheet, Consent Form and Debrief Form to reflect that this is the final part of their participation and no more communication will be required following this step. As in the cognitive interview debrief form, participants will be invited to contact the researchers should they wish to receive a copy of the final PROMs and/or report. The same mild risk of feelings of anxiety in the cognitive interview stage applies here. Similarly, participants will be fully informed of this possible risk and the reasons for the personal nature of the questions asked, as well as their right to stop their participation at any point.

References:

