Guidance by Willis on conducting and analysing cognitive interviews for questionnaire design and appraisal was followed (Willis, 2005; Willis, 2015). Anonymised verbatim transcripts of the interviews were created using speech-to-text software (Otter; <https://otter.ai>) with transcription errors manually corrected. The corresponding portions from every interview transcript for each PROM item were collated to create individual documents for each item containing all feedback pertaining to that question from across the entire sample. Top-down question feature coding was applied to these summaries using the Question Appraisal System (QAS-99) (Willis & Lessler, 1999). The systematic evaluation of every response to each PROM item for both the RUTISS and the RUTIIQ was conducted to identify potential problems, which were corrected based on verbatim quotes and interviewer field notes through collaborative analysis with the entire research team. If there were any uncertainties found in the first round of interviews about whether to include or exclude an item, the item was retained in the second round to gain further feedback. Further versions of the RUTISS and the RUTIIQ were created at this stage and used in the second interview round. The same process was undertaken after this, with an amended version created for pilot testing.

Stage 3: Online pilot testing

Data preparation and assumption testing:

Total scores were calculated for each of the Recurrent Urinary Tract Infection Symptom Score (RUTISS) subscales at Baseline and Test-Retest Assessments. Total scores for the RUTISS as a whole measure were not computed to avoid misrepresenting multidimensional constructs as a single score (Strauss & Smith, 2009). Data collected using the Urinary Tract Infection Symptom Assessment (UTISA) and Numerical Pain Rating Scale (NPRS) were scored according to their standard scoring systems.

The following assumptions were assessed: (1) normality – Shapiro-Wilk $p > .05$, so non-parametric analyses were conducted where applicable; (2) linearity – examination of scatter plots confirmed no violation; (3) multicollinearity – Variance Inflation Factor scores for the target label data as well as possible demographic characteristics were sufficiently close to 1; (4) independence of observations – Durbin-Watson statistic was approximately 2 for each subscale

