score; and (5) homoscedasticity – (inspection of the standardised residuals plotted against standardised predicted values confirmed no violation).

Case-wise diagnostics of the subscale scores indicated five possible outliers outside 3SD; however, since these were not measurement errors and could feasibly reflect true variation within the population, they were not removed. Analyses conducted with and without these cases indicated that they had no statistically significant effect on the outcomes ($p > .05$).

Statistical analyses:

Exploratory factor analysis (EFA) was conducted for both the RUTISS and RUTIIQ data. Suitability for EFA was checked through bivariate correlation matrices with coefficients greater than .80 examined for potential multicollinearity (Field, 2013). Preliminary data analyses were undertaken to assess the factorability of the dataset using Bartlett's Test of Sphericity and the Kaiser-Meyer-Olkin Measure of Sampling Adequacy (Yong & Pearce, 2013). Principal Axis Factoring was selected for application above Principal Components Analysis and Maximum Likelihood Analysis to facilitate determination of a latent factor structure (Fabrigar et al., 1999; Yong & Pearce, 2013). Varimax rotation with Kaiser Normalisation was applied to minimise cross-loading of items on factors (Fabrigar et al., 1999). Visual inspection of scree plots determined the retained number of factors, combined with evaluation of eigenvalues exceeding Kaiser's criterion of 1 (Kaiser, 1960; Watkins, 2018). Items with extracted communalities less than .40 were removed, and a minimum factor loading of .40 was defined as acceptable a priori (Fabrigar et al., 1999; Watkins, 2018).

Internal consistency was measured for each finalised post-EFA RUTISS subscale and the RUTISS as a whole measure using Cronbach's alpha (Cronbach, 1951). To assess test-retest reliability, intraclass correlation coefficients (ICC) and their 95% confidence intervals were computed based on a single-rating, absolute-agreement, two-way mixed effects model, as recommended for test-retest reliability analysis of measures intended to demonstrate outcomes at an individual (single-rater) level (Koo & Li, 2016). Construct validity was assessed by computing the level of Spearman's correlation between each RUTISS subscale and the observed UTISA and NPRS scores (Schober et al., 2018).

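### RUTISS construct validity rests on the size of correlations with UTISA and NPRS alone; with no predicted ranking and no contrast tested, no result could count against validity

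*SAP*

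**What the plan says.** Construct validity is a named secondary aim. The protocol (Research Questions, Secondary aims) plans "To validate the rUTI symptom PROM by conducting statistical tests of its internal consistency, test-retest reliability, construct validity and criterion validity".

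The instrument is designed with two parts (Protocol, Design and Procedure): "The rUTI Symptom Scale includes a UTI-related symptom intensity subscale, and a UTI-pain intensity sub-scale".

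The SAP (Stage 3, Statistical analyses) gives one sentence on the method, which is to compute Spearman's "correlation between each RUTISS subscale and the observed UTISA and NPRS scores". Under Data preparation and assumption testing, only these two comparators are scored: "Data collected using the Urinary Tract Infection Symptom Assessment (UTISA) and Numerical Pain Rating Scale (NPRS) were scored according to their standard scoring systems".

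The protocol (stage 3, online pilot) says of the survey that "there will also be a number of existing standardised measures which measure similar concepts of symptom intensity and health impact". Besides UTISA and NPRS it lists six: loneliness, work impairment, sexual distress, patient satisfaction, anxiety and depression. The SAP names none of the six.

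The SAP does fix criteria in advance elsewhere: an item content validity index of at least 0.75 with a median of at least 4, and a factor loading of at least .40.

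**The concern.** UTISA and NPRS are both measures on which a UTI symptom scale should score high. Two sizeable correlations with them are what a good subscale would show. They are also what a subscale would show if it only registered how unwell the respondent feels. The plan contains no comparison that would come out differently in the two cases.

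This is more than a missing threshold. A cut-off on the size of the coefficient would not help, because a general-severity scale can clear it too. What separates the two cases is a ranking: the pain subscale closer to NPRS than to UTISA, and the urinary-symptom subscale the reverse. The SAP declines to compute a RUTISS total because the constructs are multidimensional, so separate subscale scores depend on this distinction. At stake is whether the reported coefficients can support a claim that the two subscales measure different things.

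**Working it through.** **Inputs from the documents.** Completers of both parts: 100. Attrition: 25%. Recruitment: 132. Checking the last: 100/(1 − 0.25) = 133.3, rounded up to 134; and 132 × 0.75 = 99. The stated 132 is reproduced to within two participants. Construct validity needs Part 1 only, so both n = 100 and n = 132 are used below. The documents give no expected correlation, alpha or power for construct validity. Every correlation and loading below is an assumption.

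**1. What one coefficient shows.** The Fisher z interval for Spearman's r uses SE = √[(1 + r²/2)/(n − 3)]. For r = 0.5 and n = 100, SE = √(1.125/97) = 0.108, and the 95% CI is 0.33 to 0.64. For r = 0.7 it is 0.57 to 0.80. Neither interval says anything about specificity.

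**2. A scale driven by one general factor.** If subscale and comparators all load λ on one factor, every pairwise correlation is λ². Simulated Spearman correlations at n = 100:

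| Loading λ | λ² | Own-domain r ≥ 0.5 |
|---|---|---|
| 0.8 | 0.64 | about 95% |
| 0.7 | 0.49 | about 36% |
| 0.6 | 0.36 | about 3% |

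The 0.5 mark is illustrative, since the SAP has no such rule. In the same settings a one-sided 0.05 test that the own-domain correlation exceeds the cross-domain one passes wrongly in about 5–6%.

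**3. Power if the scale is specific.** Take own-domain 0.65, cross-domain 0.45, and a correlation c between UTISA and NPRS. The Meng–Rosenthal–Rubin statistic is

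z = (atanh r₁ − atanh r₂) × √[(n − 3)/(2(1 − c)h)], where h = (1 − f·r̄²)/(1 − r̄²), f = (1 − c)/[2(1 − r̄²)] (at most 1) and r̄² = (r₁² + r₂²)/2.

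- Here r̄² = (0.4225 + 0.2025)/2 = 0.3125, and atanh 0.65 − atanh 0.45 = 0.775 − 0.485 = 0.291.
- c = 0.2, n = 100: f = 0.582, h = 1.190, z = 2.07. Power = Φ(2.07 − 1.645) = 67%.
- c = 0.6, n = 100: f = 0.291, h = 1.322, z = 2.78. Power = Φ(2.78 − 1.645) = 87%.

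Simulated Spearman values, which are slightly attenuated, give about 63–84% at n = 100 and 74–93% at n = 132 over c = 0.2 to 0.6. These are for one contrast. If both must succeed (subscales correlated 0.5, c = 0.3 to 0.5), power is about 42–59% at n = 100 and 57–74% at n = 132.

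**4. Would the non-symptom measures do instead?** Suppose a pure severity scale, with UTISA loading 0.8 on severity and loneliness or satisfaction loading only 0.5–0.6. The severity scale still correlates more with UTISA, and passes that contrast in about 62–82% of samples of 100. This comparison therefore does not exclude a general factor.

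The same arithmetic applies to one UTISA-versus-NPRS contrast if those two load unequally, so the 5–6% in step 2 assumes equal loadings. But a pure severity scale would then pull both subscales toward the same comparator, and the mirrored contrast would fail. The pair of contrasts, read together, is what guards against the threat.

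**The case against.** **The cross-domain table is already there.** The SAP correlates each subscale with both comparators, so the coefficients needed for the main contrast will exist. This stands. A reader might infer that the method cannot in principle separate a specific subscale from a general one. The documents do not support that: what is missing is the prediction and the comparison.

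**No one has said the plan would declare success.** This also stands. A reader might infer that a finding of validity is close to guaranteed. The SAP states no pass rule, and under an assumed 0.5 rule the result depends heavily on the loading (95% down to 3%). The supportable statement is narrower: nothing in the plan could make the claim fail.

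**Other evidence exists.** Content validity indices, cognitive interviews and EFA all bear on the subscales, and a single dominant factor among the items would tend to show in the scree plot. That is fair, and it rules out saying that the subscales would have no support. But EFA relates the instrument's own items to one another, varimax keeps the factors uncorrelated by construction, and the regressions concern demographics and the rating of change. None compares a subscale with an outside measure of a different construct.

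**A valid scale may fail the contrast.** The protocol's Background lists painful or burning urination among UTI symptoms, so a sound pain subscale may also follow UTISA. The two-subscale structure is also the pre-EFA version. Both points stand and are carried into the fix.

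**Conclusion.** The point holds as a cheap and worthwhile improvement. The SAP's test of a named secondary aim has no outcome that would count against validity, and it does not distinguish a subscale specific to urinary symptoms or pain from one that follows general severity. This rests on the SAP's text and needs no assumption.

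The size of the problem cannot be fixed from the documents. The figures above depend on assumed loadings and correlations, on equal comparator loadings for the 5–6%, and on a one-sided 0.05 test.

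Two stronger readings should be resisted. First, nothing here shows that the RUTISS in fact measures general severity. Second, a reader might infer that the six unused scales would settle the matter; step 4 shows that they would not by themselves. That they were collected is also only planned in the protocol, and the SAP does not confirm it.

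**What to change.** In the SAP's construct-validity paragraph, for the post-EFA subscales and using all Part 1 responders:

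- **Main test.** State that the urinary-symptom subscale correlates more with UTISA than with NPRS, and the pain subscale more with NPRS than with UTISA. Test each difference with a dependent-correlation test or a bootstrap CI, and read the two together. If EFA yields other subscales, restate the mapping first.
- **Supporting evidence only.** State that each own-domain correlation exceeds that subscale's correlation with loneliness and with patient satisfaction. Say that this does not by itself exclude a general-severity factor.
- **Reporting.** Give expected directions, 95% CIs for all coefficients and differences, and a rule set beforehand for what share of confirmed hypotheses counts as support.
- **Status.** The SAP is written in the past tense and already reports some findings. If the data have been seen, label the hypotheses post hoc.

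The cost is SAP wording and a few further correlations on data the protocol already plans to collect, with no extra participants or questionnaires. The downsides are real. The validity claim can now fail. Power for a gap of 0.20 is moderate for one contrast and lower for both. A failed contrast for the pain subscale needs careful interpretation, because pain on urination is itself a UTI symptom.
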